## Time Frame for the Study

For the Main study, TEAMS launched its participant recruitment in October 2017 and ended participant enrollment in 2019. **Figure 4** shows the timeline for a few of the major milestones completed during the study period. Recruitment for the rDirectCAM group (Enhancement study) was not necessary as we had interested participants who already signed up the study via our website or through our clinic partners but were not able to enroll before the Main study needing to be ceased due to the pandemic. We established a protocol for conducting the teleassessments and tele-training and developed a structured set of procedures for equipment purchase and shipping/scheduling based on the Enhancement supplement received in May 2020. We began participant screening for the Enhancement study on September 10, 2020, with 100% enrollment completed on March 22, 2021. The study was closed on November 1, 2021.

**Figure 4. Major Milestone Completion Timeline of the Main Study**

**Table 5** provides an overview of the timeline for the data collection, intervention, and regular check-ins of the Main and Enhancement studies.

**Table 5 Overview of the Data Collection, Intervention, and Check-ins Timeline for the Main and Enhancement Studies**

	Main Study	Main Study	Enhancement
Assessment time point	DirectCAM	TeleCAM	rDirectCAM
Month 0	Baseline assessment (on-site)	Baseline assessment + Training (on-site)	Baseline assessment (real-time via video conference)
Months 1 to 2	Biweekly sessions (on-site)	Biweekly new videos (at-home) + IVR calls weekly	Biweekly sessions (real-time via video conference)
Month 3	Weekly sessions (on-site)	Weekly new videos (at-home) + IVR calls weekly	Weekly sessions (real-time via video conference)
End of Month 3 (post intervention: 12 weeks)	3 month assessment (on-site)	3 month assessment (on-site)	3 month assessment (real-time via video conference)
End of Month 6	6 month assessment (on-site)	6 month assessment (on-site)	6 month assessment (real-time via video conference)
End of Month 12	1 year assessment (on-site)	1 year assessment (on-site)	NA
Months 4 to 12	Continue to exercise (at-home)	Continue to exercise (at-home) + IVR calls 4-5 months weekly/ 6-12 months biweekly	Continue to exercise (at-home)

## Data Collection and Sources

Study data were collected by the therapists at the clinic sites via paper and scanned into a secure cloud storage environment Box approved for UAB investigators. The data were then transferred and managed using REDCap (Research Electronic Data Capture). REDCap is a secure, web application designed to support data capture for research studies, providing user-friendly, web-based case report forms, real-time data entry validation (e.g., for data types and range checks), audit trails and a de-identified data export mechanism to common statistical packages (SAS version 9.4, R version 4.3.2 ). Network transmissions (data entry, survey submission,

web browsing, etc.) in REDCap are protected via Secure Sockets Layer (SSL) encryption. All data was quality checked by different team personnel to detect and correct data entry errors.

Missingness in the weekly feedback, monthly motivational, and clinic assessment data stored in the REDCap database was tracked periodically. Data were imported into the REDCap server on a weekly basis and queried for missingness. Reminder calls were sent to participants to reduce missed appointments and to remind participants to respond to IVR calls in TeleCAM. If more than 2 data points were missed, the study team called both therapists and participants to inquire why, and to reengage as many as possible and retrieve the missing data. Clinics were provided with checklists to ensure that all measures were collected at each assessment session in a consistent order according to study protocol. Checklists minimized data loss due to technical difficulties. Missed appointments were rescheduled immediately. Reasons for drop-out (and whether drop-out was therapist or participant-initiated) were documented in detail in Box, REDCap and in the monthly CONSORT diagram. To minimize loss to follow-up, multiple types of contact information were collected. Protocols were developed by our stakeholders for contacting participants in an approachable nature throughout the study through both telephone and emails.

## Analytical and Statistical Approaches

### **Main Study**

Our analysis was following ITT protocol as all participants assigned to the randomized clinics and completed baseline assessment were included in the analysis.

Our primary hypotheses were about comparing the change in the 11 outcomes (listed in **Table 4**) between baseline and 12th month follow-up across the two arms. We considered these 11 hypothesis tests for the 11 outcome variables as part of a single family of hypotheses. We employed the Holm-Bonferroni method for controlling the overall family wise error rate and computed adjusted *p*-values. For each outcome we used a linear mixed effects model, with TeleCAM arm as the reference category, and accounting for the correlated nature of the data due to the nesting of participants within a clinic as random effects. Crude models included fixed effects included both Arms (TeleCAM, DirectCAM), Time (baseline [reference], 3 month, 6 month, 12 month), an Arms X Time interaction, and accounted for randomization strata (clinic location being urban vs. non-urban). The interaction of Arms and Time variables was the primary effect of interest since it quantified the differences within Arm change in the outcome from baseline over time of the two Arms. For example, based on the fitted model that included the interaction between Arm and Time, the difference in change over time from baseline to 12 months between DirectCAM and TeleCAM were estimated. Contrast statements were used to test the null hypotheses in conjunction with the fitted model coefficients and standardized differences in the average treatment effect reported. The estimates of the change in health and function outcomes for each arm and their 95% confidence interval were also reported. As a sensitivity analysis, similar models additionally adjusted for sex, race, and post-COVID data collection measure indicated were also ran. Note that, since post-COVID, data collection for patient reported outcomes was conducted remotely for remaining participants, the former was also included as a covariate in the adjusted model. Next, missingness in primary and secondary outcomes were addressed using multiple imputation technique (MCMC) via PROC MI in SAS,

assuming missing at random. Additional sensitivity analyses were conducted using wild bootstrap to assess the robustness to model assumptions.

The estimated changes between groups and within groups were then compared to minimally clinically important difference (MCID) published in literature for the studied outcomes among people with MS. For primary outcomes, the published MCID was for MFIS= 4 and SF-36 pain score = 4.9. For secondary outcomes, MCID for 6MWT= 21.56, BBS= 3, TUG= 10.6, FTSTS= 13 and grip strength= 10.5. For exploratory outcomes, MCID was published for SF-36 physical functioning (MCID= 7.1).

Aim 2 was about evaluating pre-specified confirmatory HTE analyses by testing the role of 4 prespecified moderators (age, geographic location/residence based on participants zip codes, type of MS and severity of MS) on each of the primary self-reported outcomes: MFIS, SF-36 MCS, SF-36 PCS, SF-36 pain domain scale, and GLTEQ. We had 4 families of hypothesis tests within this aim – one for every moderator with 2 levels (PDDS 0-3 [without assistive devices] and PDDS 4-7 [with assistive devices]). Our model was like the one used in the primary aim except that we augmented the model with an additional two-way interaction term between moderator (e.g., education level) and Arm (moderator X Arm), and a 3-way interaction term between moderator x Arm x Time. When a 3-way interaction was observed, post-hoc tests were performed to determine the differential influence of the moderator to one treatment versus another, controlling for family-wise error utilizing the Holm-Bonferroni method. We expected no greater than 11 post-hoc tests per pre-specified moderator and used contrast statements to achieve this. Our missing data strategy was similar to that in the primary aim.

We examined the role of SCT construct variables (social support, outcome expectancies, self-efficacy, self-regulation) as mediating variables between the intervention and primary outcomes. As part of our tertiary aims, we had 4 families of hypotheses, one for each mediating variable listed in **Table 4**. Each family of hypotheses had 5 hypotheses tests, one for each primary outcome. We applied the product of coefficients test framework as our primary approach to compute the mediated effects for each of the primary outcomes as suggested by MacKinnon. Additionally, we did mediation analysis for the 6 secondary and the 7 exploratory outcomes. Note that these analyses were conducted using multiple imputed datasets created for aim 1 sensitivity analyses.

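### The primary 12-month contrast leaves out baseline-outcome adjustment and so some precision (SE cut of about 6-10% at the plan's correlation of 0.3), and its inference should be tied to clinic-level variation

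*Combined protocol and SAP*

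**What the plan says.** Under Analytical and Statistical Approaches, Main Study, one linear mixed model is fitted per outcome. Its fixed effects include Arm, "Time (baseline [reference], 3 month, 6 month, 12 month), an Arms X Time interaction", and the urban/non-urban randomization stratum. Baseline is therefore part of the response, with its own Arm effect. The primary quantity is the interaction contrast at month 12: "the difference in change over time from baseline to 12 months between DirectCAM and TeleCAM were estimated".

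The sensitivity analysis uses "similar models additionally adjusted for sex, race, and post-COVID data collection measure". The baseline outcome is not among these additions.

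Clustering is described only as "accounting for the correlated nature of the data due to the nesting of participants within a clinic as random effects". No clinic-by-time effect, participant-level covariance across visits or degrees-of-freedom method is named. The section adds that "Additional sensitivity analyses were conducted using wild bootstrap to assess the robustness to model assumptions", without saying whether clinics or participants are the resampling unit.

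The same contrast serves the whole testing family: "We considered these 11 hypothesis tests for the 11 outcome variables as part of a single family of hypotheses", with Holm-Bonferroni adjustment. The analysis set is defined so that "all participants assigned to the randomized clinics and completed baseline assessment were included in the analysis", and "missingness in primary and secondary outcomes were addressed using multiple imputation technique (MCMC) via PROC MI in SAS" under missing at random.

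**The concern.** When the correlation between visits is modest, subtracting the full baseline value adds noise that a regression on baseline would avoid. The plan's own assumed correlation is 0.3, and every participant in the analysis set has a baseline assessment. Precision is thus left unused in all 11 tests.

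The second issue is how uncertainty is measured. Clinics were randomized. Participant and clinic intercepts both cancel from a change-from-baseline contrast. If those were the only random effects, the standard error carries no between-clinic variation in change, although the clinic is the level at which arms were assigned. The documents give some reason to expect such variation. DirectCAM was delivered by therapists at each clinic, and on-site delivery and testing moved to remote part-way through. They give no size for it.

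**Working it through.** **Inputs.** 40 randomized clinics (Study Overview). ICC 0.05, correlation 0.3, 533 completers, 820 enrolled and 35% attrition (Sample Size Calculations and Study Power). Correlation 0.7 is the Enhancement study value in the same section, used as an upper range. Eleven tests give a first Holm step of 0.05/11 = 0.00455.

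Assumed here: 20 clinics per arm, equal clinic sizes, outcome variance 1.

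**The plan's figures.** 820 x 0.65 = 533. Per clinic, 533/40 = 13.3 and 820/40 = 20.5, taken as 13 and 20. The formula behind 533 is not given, and nothing below depends on it.

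**Step 1: change contrast (correlation 0.3, stable clinic effects).** The variance splits into clinic 0.05, participant 0.25 and visit 0.70. The variance of one participant's change is 2 x 0.70 = 1.40. With 13 per clinic, SE = sqrt(2 x (1.40/13)/20) = 0.1038.

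**Step 2: adjusted contrast.** With the clinic-mean baseline in the model, the arm effect is estimated from clinic means.
- Variance of a clinic mean: V = 0.05 + 0.95/13 = 0.1231.
- Covariance of baseline and month-12 clinic means: C = 0.05 + 0.25/13 = 0.0692.
- Correlation of clinic means: C/V = 0.5625.
- Residual variance: V x (1 - 0.5625^2) = 0.0841.
- SE = sqrt(2 x 0.0841/20) = 0.0917. Estimating the slope from 40 clinics multiplies this by about sqrt(1 + 1/36) = 1.014, giving 0.0930.
- Reduction: 1 - 0.0930/0.1038 = 10%.

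The attrition rows assume 20 enrolled per clinic, with 18, 15 and 13 seen at months 3, 6 and 12. They come from a generalised least squares calculation averaged over simulated baselines.

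**Step 3: cost of clinic-level degrees of freedom.** 40 clinics less intercept, arm, clinic-mean baseline and stratum leave 36. Critical values are 2.028 against 1.960 (ratio 1.035) at 5%, and 3.027 against 2.838 (ratio 1.067) at the first Holm step. The last two columns give the width of the adjusted interval on t(36) relative to the change contrast on z. Using z for the current contrast is an assumption, since no reference distribution is stated.

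| Correlation | Per clinic | SE, change | SE, adjusted | SE cut | Width ratio, 5% | Width ratio, first Holm step |
|---|---|---|---|---|---|---|
| 0.3 | 13 | 0.1038 | 0.0930 | 10% | 0.93 | 0.96 |
| 0.3 | 20 | 0.0837 | 0.0769 | 8% | 0.95 | 0.98 |
| 0.3 | attrition | 0.0963 | 0.0908 | 6% | 0.98 | 1.01 |
| 0.7 | 13 | 0.0679 | 0.0655 | 3.5% | 1.00 | 1.03 |
| 0.7 | 20 | 0.0548 | 0.0533 | 2.7% | 1.01 | 1.04 |
| 0.7 | attrition | 0.0644 | 0.0635 | 1.4% | 1.02 | 1.05 |

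**Step 4: what an intercept-only standard error omits.** Let A be the clinic autocorrelation between baseline and month 12 (assumed). Hold the total correlation at 0.3, with 13 per clinic. The variance of a clinic's mean change is 2 x 0.05 x (1 - A) + 2e/13, where e = 0.95 - (0.3 - 0.05A).
- A = 1: 1.40/13 = 0.1077, true SE 0.1038.
- A = 0.8: 0.02 + 1.38/13 = 0.1262, true SE 0.1123.
- A = 0.5: 0.05 + 1.35/13 = 0.1538, true SE 0.1240.

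With participant and clinic intercepts the model SE stays at 0.1038. The size of a nominal 5% test is 2 x Phi(-1.96 x model SE/true SE), which gives 5.0, 7.0 and 10.1%. At the first Holm step (nominal 0.45%) it is 0.45, 0.87 and 1.76%. A simulation of 20,000 trials gave 5.0, 7.1 and 10.0% at the 5% level. A clinic-mean baseline-adjusted t test on 37 df, without the stratum, held 5.0, 5.1 and 4.9%.

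If only DirectCAM clinics vary, the variance averages the two arms. At A = 0.8, (0.1262 + 0.1077)/20 gives SE 0.1081 and size 6.0%. At A = 0.5 the size is 7.5%.

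With a clinic intercept only, model SEs are 0.1200, 0.1204 and 0.1211. Their ratios to the true SEs are 1.16, 1.07 and 0.98.

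**The case against.** The plan's hypothesis is about change, and the interaction estimates exactly that. Nothing is misaligned, and a reader who inferred that the primary contrast is biased or invalid would be going beyond the documents. The gain is modest. Against a z-based test it is nearly gone at a correlation of 0.3 with 35% attrition (0.98 at 5%, 1.01 at the first Holm step), and at 0.7 the interval is no narrower or is wider. It also depends on the form of adjustment: a single-slope individual ANCOVA can lose it (variance ratio 0.97 at 20.5 per clinic with stable clinic effects). All of this stands. It is why the clinic-mean baseline belongs in the model and why the fair comparison puts both contrasts on the same degrees of freedom.

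A reader might also infer that the trial's type I error is inflated. The documents do not support that. It needs both an intercept-only model and a clinic autocorrelation below 1, and neither is stated. Clinic-delivered therapy applies to DirectCAM only, was standardised by manual and checklist, and was followed by nine months of home exercise. The sensitivity model already has a post-COVID collection term, though this captures an average shift rather than differences between clinics. A family-wise error as high as 17.7% can be calculated, but only with 11 independent outcomes and autocorrelation 0.5 in every one. Independence is untenable when the SF-36 component scores and pain come from the same subscales.

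The planned wild bootstrap would cover the omission if clustered by clinic. Its unit is unstated, and it is only a sensitivity analysis.

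**Conclusion.** The point holds as one of efficiency, with a safeguard attached. On the same clinic-level degrees of freedom, adjustment for individual and clinic-mean baseline cuts the standard error by about 6-10% at correlation 0.3 and 1-4% at 0.7. This rests on 40 equal clinics in two equal arms, ICC 0.05, stable clinic effects and, for the lower ends, an assumed dropout path.

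The standard-error issue is conditional. Its size may be zero, and its direction depends on which random effects were fitted. It justifies inference that includes clinic-level variation, but not a claim that the reported p-values are wrong. The change should be made, with medium confidence in its practical effect.

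**What to change.** Report, beside the change contrast, a 12-month arm contrast adjusted for individual baseline outcome, clinic-mean baseline outcome and the urban/non-urban stratum. Keep the ITT set by handling participants without follow-up through the planned multiple imputation, with baseline and clinic in the imputation model. Otherwise those with baseline data only would drop out of the adjusted model (2 of 20 per clinic, 10%, on the assumed path). The study closed in November 2021, so if results are known the analysis must be labelled post hoc and not replace the planned contrast.

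Base inference on clinics. Either cluster the planned wild bootstrap by clinic, or add a clinic-by-time random effect with small-sample degrees of freedom and a named fallback if its variance is estimated at zero. State the random effects fitted and the participant-level covariance across visits.

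The cost is one extra analysis per outcome and a few sentences in the SAP. Critical values widen by about 3% at 5% and 7% at the first Holm step, which can cancel the precision gain relative to z. Assignment was by clinic and not blinded to participants or delivery staff. If baselines differ systematically between arms, the two contrasts may disagree and neither is automatically unbiased, so both should be shown.

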### Study Overview

The TEAMS study was a cluster randomized, comparative effectiveness trial comparing the effectiveness of TeleCAM and DirectCAM delivered at 43 clinics across Alabama, Mississippi, and Tennessee. There were 40 clinics initially randomized and 3 satellite sites including Cookeville, Ashland City and Mobile were added later. These 3 satellite sites were not randomized as they were close to and were associated with support groups at the existing randomized sites. The satellites sites were recruited to alleviate logistical challenges in throughput around baseline testing after enrollment.

Using the clinics as the units of randomization, our criteria while identifying clinic sites were to minimize the risk of contamination while having enough sites for a cluster randomization, ability to detect a small to moderate effect size, and ability to recruit efficiently. The randomization list was run by a study statistician who was not involved in any participant interaction and intervention delivery. Given the nature of this study design, group assignments were not blinded to participants and study staff involved in the intervention delivery but were blinded to data analysts.

[figure not shown]

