**TeleCAM.** The TeleCAM participants received the same intervention content as DirectCAM. The only difference was that the TeleCAM participants received the intervention via exercise videos preloaded to a tablet that was given to them upon enrolling in the study. The exercise videos were filmed with a person with MS instructing and demonstrating the CAM program. Each TeleCAM participant began with one onsite training session with a study therapist. In the training session, participants were shown how to turn the tablet on and off to watch the videos, perform the basic exercises correctly, and use the yoga and Pilates equipment. Participants were asked to bring a family member or friend with them in case they needed assistance using the tablet. The TeleCAM participants were contacted by an Interactive Voice Response (IVR) system-initiated call at their preferred dates and times (aligned with the general intervention timeline) to promote adherence to the yoga/Pilates exercise and neurorehabilitation practice. The IVR system is an automated communication system that includes computers, specialized phone hardware, and operating software to allow immediate computer-assisted interaction with participants by telephone. It was developed during our research team's past physical activity research and in the current study was adapted to address the specific concerns of individuals with MS (physical activity progress, pain, fatigue, and key motivational variables from the SCT). The IVR calls were sent to only

TeleCAM participants weekly for the first six months, and then biweekly for months 6-12 to monitor physical activity, pain, fatigue, and quality of life for SCT variables.

**rDirectCAM.** The rDirectCAM was developed in response to the Covid-19 pandemic and was the Enhancement study intervention. Participants enrolled in rDirectCAM received the same intervention as DirectCAM. The only difference was that the rDirectCAM participants utilized a remote platform at home to work synchronously with a therapist.

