### Potential covariates

In addition to age, sex, education-level, height, and race, which were collected at baseline, information on all participants' time-varying covariates were collected through a questionnaire at baseline and the three follow-up time points. These covariates included: weight, type of MS, prescribed and non-prescribed medications, distance from the clinic

(address), caregiver support, assisted devices, PDDS. The type of MS, PDDS, age and geographic locations based on participants zip code (urban/non-urban) were our prespecified moderators for the study outcomes.

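### The Main Study's adjusted sensitivity model omits baseline PDDS, age, MS type and distance, and describes no covariate-by-Time terms, so it can say little about differential recruitment under open clinic allocation

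*Combined protocol and SAP*

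**What the plan says.** Study Overview: clinics are the unit of randomisation ("There were 40 clinics initially randomized"), and "group assignments were not blinded to participants and study staff involved in the intervention delivery". Three satellite sites joined later without being randomised.

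Analytical and Statistical Approaches, Main Study: the analysis set is defined by "all participants assigned to the randomized clinics and completed baseline assessment were included in the analysis". The linear mixed model has Arm, Time, Arm by Time, the urban/non-urban clinic stratum, and random effects for participants nested within clinics. On the estimand: "The interaction of Arms and Time variables was the primary effect of interest". The covariate check is that "similar models additionally adjusted for sex, race, and post-COVID data collection measure indicated were also ran". Missing outcomes are multiply imputed under missing at random. The variables in the imputation model are not listed.

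Potential covariates: age, sex, education, height and race are taken at baseline. A further set is taken at baseline and at all three follow-ups: "These covariates included: weight, type of MS, prescribed and non-prescribed medications, distance from the clinic", then caregiver support, assistive devices and PDDS.

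Age, MS type, PDDS and zip-code residence enter Arm-by-Time models only in Aim 2, as effect modifiers and only for the five primary self-reported outcomes. Distance appears in no listed model. The Enhancement Study section plans propensity-based weighting on observed baseline covariates. The Main Study section plans nothing of that kind.

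**The concern.** Randomising clinics balances clinics in expectation. It does not balance the people who join once a clinic's arm is known. The arms ask for different amounts of travel. The DirectCAM description and Table 5 imply 20 on-site sessions plus 4 on-site assessments (24) for DirectCAM. TeleCAM has the 4 assessment visits, with training at the first. Distance and disability could therefore plausibly influence who enrols, who completes the baseline assessment needed to enter the analysis set, and who stays.

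If such a characteristic differs by arm and also predicts 12-month change, the Arm-by-Time contrast mixes recruitment with treatment. The covariate-adjusted analysis is where a reader would look for reassurance. As described, it holds neither the most relevant collected variables nor the terms through which a baseline variable could alter that contrast.

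**Working it through.** **Design figures reproduced.** Sample Size Calculations and Study Power gives 0.00625 per test and 820 enrolled: 0.05 / 8 = 0.00625 and 533 / (1 − 0.35) = 820. Both agree. The same section gives the 0.2 effect size, 80% power and the 0.3 correlation among repeated measures used below. The plan gives no figure for imbalance or confounding, so those inputs are assumed.

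**Which terms matter.** Let x be a fixed baseline covariate.

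- As a main effect, x shifts a participant's outcome equally at every visit. It cancels from change since baseline, so with complete data the Arm-by-Time estimate cannot move. In a simulated dataset the estimate was 0.1288 without x, 0.1288 with x as a main effect, and 0.0139 with x crossed with Time (true value 0).
- Sex and race are fixed covariates, so as described they can move the contrast only through the pattern of missing visits. The post-COVID collection indicator varies over time and can move it, but it addresses mode of collection and not recruitment.

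**Size of the bias.** Bias in the contrast = (arm imbalance in x, in SDs of x) × (effect of x on 12-month change, in outcome SDs per SD of x).

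Assumed ranges: imbalance 0.1 to 0.3; effect 0.1 to 0.4.

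| Imbalance | Effect on change | Bias (SD) | Share of 0.2 |
|---|---|---|---|
| 0.1 | 0.1 | 0.01 | 5% |
| 0.2 | 0.3 | 0.06 | 30% |
| 0.3 | 0.4 | 0.12 | 60% |

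The plan does not say which SD scales the 0.2. If it is the SD of change, then with correlation 0.3 that SD is √(2 × (1 − 0.3)) = 1.183 outcome SDs. The target becomes 0.2 × 1.183 = 0.237 outcome SDs, and the shares become 0.01/0.237 = 4% to 0.12/0.237 = 51%.

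**Effect on the error rate.** The standard error implied by the plan's own target is 0.2 / (2.734 + 0.842) = 0.0559. For a two-sided test at 0.00625, type I error under bias b is Φ(b/SE − 2.734) + Φ(−b/SE − 2.734).

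- b = 0.01: 0.0071
- b = 0.06: 0.048
- b = 0.12: 0.278

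These depend on the small SE. For a simple baseline-to-month-12 change in 533 completers, ignoring clustering, SE = √(4 × 1.4 / 533) = 0.1025, and the same three biases give 0.0065, 0.016 and 0.059. The size of the bias is the same; it is simply less visible against a wider standard error.

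**Does the proposed adjustment work?** In 4,000 simulated trials with 280 per arm, imbalance 0.2 and effect 0.3, the mean unadjusted contrast on change was 0.060. Adjusting change for x, which is equivalent to crossing x with Time, gave 0.000. The spread of the estimates was essentially the same (0.099 against 0.097).

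**The case against.** **Timing is inferred.** No sentence says when a person learned the clinic's arm relative to consent. Lack of blinding does not settle it. Nor does the tablet "preloaded to a tablet that was given to them upon enrolling in the study", because the Interventions section says equipment was handed out after baseline testing and mentions the tablet alongside it. This objection stands: enrolment after allocation is likely in an open clinic-randomised design, but it should be worded as a risk.

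**The contrast already protects.** Stable differences in outcome due to PDDS or age cancel in change from baseline, and the clinic stratum is in the model. This also stands, and it narrows the point to covariates that both differ by arm and predict change. The stratum describes the clinic's location, not the participant's travel.

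**Aim 2 covers some of it.** For the primary outcomes, the moderator models show the arm contrast within levels of age, MS type and severity. They are not an adjusted overall contrast, they leave out distance, and they do not cover the secondary outcomes.

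**Travel differs in degree only.** TeleCAM participants also came to the clinic for assessments. This is correct, and nothing in the document shows that the difference altered recruitment.

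**Missing data.** A reader might infer that predictors of dropout were left out of the imputation. The document does not support that: the imputation variables are unlisted, not shown to be absent, and 35% is a planning assumption for attrition.

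**Conclusion.** The point holds as a gap in the sensitivity analysis. Four collected baseline variables that could plausibly relate to recruitment and change are absent from the Main Study arm comparison, and no covariate-by-Time terms are described.

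Under the assumed inputs the bias could be anywhere from negligible (0.01 SD) to more than half the design effect (0.12 SD). The range shows that the question is worth checking. It does not estimate what happened.

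Two stronger readings are not supported. A reader might infer that the arms were in fact imbalanced and the primary estimate is biased, but the document reports neither imbalance nor covariate effects. A reader might also infer that a fully adjusted model should become the main estimate. The document is written in the past tense and reports study closure in November 2021, so replacing the specified model with a newly chosen covariate set would be a post hoc change to the primary analysis.

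**What to change.** 1. Extend the adjusted sensitivity model in the Main Study section to include baseline PDDS, age, type of MS and distance from the clinic, each with its interaction with Time. Use baseline values only: PDDS, MS type and distance are also collected at follow-up, and adjusting for later PDDS could remove part of the treatment effect.
2. Give sex and race the same Time interactions, or state that as main effects they are not expected to alter the contrast.
3. List the imputation variables and include these four.
4. Report the extended model beside the specified primary model without replacing it, and label it post hoc if results are already known.
5. State when each clinic's arm became known relative to consent, and tabulate baseline characteristics by arm with standardised differences.

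Cost: no new data. Item 1 adds at least 4 × (1 main effect + 3 Time interactions) = 16 terms per outcome, and more if MS type has over two levels, for 11 outcomes. Some missing covariate values will need imputing. Adjustment cannot remove selection on unmeasured traits such as motivation, so agreement between the two models would be reassuring but not conclusive.
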